6.3 Lifestyle Restrictions

Participants are advised to protect against sun exposure through sun avoidance, use of protective clothing (long sleeves, pants, hats, etc), and use of sunscreen from at least 1 week prior to the first dose of study intervention until the safety follow-up visit. Participants should avoid excessive sun exposure or use of tanning booths or other ultraviolet light sources and avoid risks that are known to provoke flare of psoriasis.

6.4 Screen Failures

Screen failures are defined as participants who consent to participate in the clinical study but who are not subsequently randomized in the study/included in the analysis population.

A minimal set of screen failure information is required to ensure transparent reporting of screen failure participants, to meet the Consolidated Standards of Reporting Trials (CONSORT) publishing requirements, as applicable, and to respond to queries from regulatory authorities. Minimal information includes date of consent, demography, screen failure details, eligibility criteria, and any serious adverse events (SAEs) that occurred following consent.

6.4.1 Re-testing During Screening

This study permits the re-enrollment of a participant who has discontinued the study as a screen failure (ie, participant has not been randomized/has not been treated). If re-enrolled, the participant must be re-consented.

Re-testing of laboratory parameters and/or other assessments within any single screening or lead-in period will be permitted once (in addition to any parameters that require a confirmatory value).

The most current result prior to randomization is the value by which study inclusion will be assessed because it represents the participant's most current clinical state.

Laboratory parameters and/or assessments that are included in Table 2-1, Screening Procedural Outline, may be repeated in an effort to find all possible well-qualified participants. Consultation with the Sponsor Medical Monitor may be needed to identify whether repeat testing of any particular parameter is clinically relevant.

7 STUDY INTERVENTION(S) AND CONCOMITANT THERAPY

Study intervention is defined as any investigational intervention(s), marketed product(s), placebo, procedure(s), or medical device intended to be administered to a study participant according to the study protocol.

Study intervention includes both Investigational [Medicinal] Product (IP/IMP) and Non-investigational/Auxiliary [Medicinal] Product (Non-IP/Non-IMP/AxMP) as indicated in Table 7.1-1.

An IP, also known as an IMP in some regions, is defined as a pharmaceutical form of an active substance or placebo being tested or used as a reference in a clinical study, including products already with a marketing authorization but used or assembled (formulated or packaged) differently from the authorized form, used for an unauthorized indication, or when used to gain further information about the authorized form.

Other medications used as support or escape medication for preventative, diagnostic, or therapeutic reasons, as components of the standard of care for a given diagnosis may be considered Non-IMPs/AxMPs.

7.1 Study Interventions Administered

Participants will receive BMS-986322 and/or placebo tablets to be taken at home. Participants will be provided by the Investigator Site with enough tablets to cover the treatment interval between study visits beginning on Study Day. Additional tablets covering the treatment interval between study visits should be supplied by the Investigator Site during each applicable follow-up visit. At follow-up visits (Days), doses of BMS-986322 and/or placebo tablets will be administered in the clinic (see Section 2).

In the morning of visits on Days (Table 2-2), each participant will receive a single oral dose of BMS-986322 and/or placebo at approximately 9:00 AM. Participants will be required to fast for at least 8 hours prior to study visit on Days.

At the time of dosing, 240 mL of water will be administered to the participant along with his/her dose of study intervention. The time of dose administration will be called "0" hour.

[figure not shown]
Table 7.1-1: Study Intervention(s) Administered

Type/ Intervention Name/Dose Formulation	Unit Dose Strength(s)	IMP/Non-IMP/AxMP Blinded or Open-label Use	Sourcing	Packaging and Labeling	Current/ Former Name(s) or Alias(es)	Storage Conditions (Per Label)
BMS- 986322-01	m g	IMP Blinded	Provided centrally by the Sponsor	Study interventions will be provided in bottles	BMS- 986322- 01	Refer to the label on the container and/or Pharmacy Manual.
Placebo to Match BMS- 986322-01	N/A	IMP Blinded	Provided centrally by the Sponsor	Study interventions will be provided in bottles	BMS- 986322- 01	Refer to the label on the container and/or Pharmacy Manual.

Abbreviations: AxMP, Auxiliary Medicinal Product; IMP, Investigational Medicinal Product; N/A, not applicable.

Table 7.1-2: Study Arm(s)

Arm Title/ Arm Type	Route of Administration
Placebo	Oral
16 mg BMS-986322	Oral
32 mg BMS-986322	Oral
64 mg BMS-986322	Oral

7.2 Assignment to Study Intervention

All participants will be centrally randomized using Interactive Response Technology (IRT). Before the study is initiated, each user will receive log-in information and directions on how to access the IRT.

During the screening visit, the investigative site will call into the enrollment option of the IRT designated by Bristol-Myers Squibb Company (BMS) for assignment of a participant number that will be unique across all sites. Enrolled participants, including those not dosed, will be assigned sequential participant numbers starting with sequential participant numbers starting with sequential numbering may restart at second for each participating site as the distinct participant identification number (PID) will ultimately be composed of the site number and participant number. For example, the first participant screened (ie, enrolled) at site number will have a PID of

Once it is determined that the participant meets the eligibility criteria following the screening visit, the investigative site will call the IRT to randomize the participant. Randomization numbers will be assigned prior to dosing. Participants will be randomized to receive either BMS-986322 at one of the doses being evaluated (16 mg PO QD, 32 mg PO QD, 64 mg PO QD) or placebo according to a computer-generated randomization scheme prepared by an IRT Manager within the Drug

Supply Management Department of BMS Research and Development. Randomization will be stratified by previous treatment with a biologic (yes/no). Block randomization with fixed block size per stratum will be employed in this study.

Study intervention will be dispensed at the study visits listed in the Schedule of Activities (Section 2).

Participants will not be replaced if they are discontinued from the study secondary to an AE unless the AE can be determined to be unrelated to treatment. If a participant is replaced after dosing, then the replacement participant will be assigned the original participant's number plus. The replacement participant will receive the same treatment as the participant being replaced, but a new randomization number will be assigned to him/her. For example, Participant would be replaced by Participant data

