7.3 Blinding

This is a randomized, double-blind, placebo-controlled study. Blinded intervention assignments will be managed using IRT. IP supply will be controlled by IRT at each visit. Access to treatment codes will be restricted from all site and Sponsor personnel and participants prior to database lock for the final analysis with exceptions as specified below. Treatment codes may be shared with sites and participants after finalization of the CSR.

Randomization schedules will be shipped directly to a pharmacist or other individual(s) who will be responsible for the dispensing of blinded study intervention. This (these) individual(s) will be unblinded to study intervention identification but will not be involved in any other aspect of study conduct. The randomization schedules will be maintained in a secure location with access limited to authorized personnel.

Blinding of study intervention assignment is critical to the integrity of this clinical study. However, in the event of a medical emergency or pregnancy in an individual participant in which knowledge of the IP is critical to the participant's management, the blind for that participant may be broken by the investigator. The participant's safety takes priority over any other considerations in determining whether a treatment assignment should be unblinded.

Before breaking the blind of an individual participant's treatment, the investigator should determine that the unblinded information is necessary (ie, that it will alter the participant's immediate management). In many cases, particularly when the emergency is clearly not related to the IP, the problem may be properly managed by assuming that the participant is receiving the IP. It is highly desirable that the decision to unblind treatment assignment be discussed with the Medical Monitor, but the investigator always has ultimate authority for the decision to unblind. The actual task of unblinding can be delegated by the investigator to a designee assigned the task on the Delegation of Authority. The Principal Investigator or appointed designee should only perform the emergency unblinding after the decision to unblind the participant has been documented.

For this study, the method of unblinding for emergency purposes is IRT.

In cases of accidental unblinding, contact the Medical Monitor and ensure every attempt is made to minimize additional disclosure and the impact of unblinding.

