8.2.1 Individual Discontinuation Criteria

- A participant may withdraw completely from the study at any time at his/her own request, or may be withdrawn at any time at the discretion of the investigator for safety, behavioral, compliance, or administrative reasons. This is expected to be uncommon. Stopping study intervention is not considered withdrawal from the study.
- At the time of discontinuing from the study, if possible, an ET visit should be conducted, as shown in the Schedule of Activities. See the Schedule of Activities (Section 2) for data to be collected at the time of study discontinuation and follow-up and for any further evaluations that need to be completed.
- The participant will be permanently discontinued from both the study intervention and the study at that time. No follow-up visit will be performed where a participant withdraws consent.
- If the participant withdraws consent for disclosure of future information, the Sponsor may retain and continue to use any data collected before such a withdrawal of consent.

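### Section 7.2 lets a replacement inherit the replaced participant's arm instead of being randomized; the effect is small, and a randomized top-up is a cheap improvement

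*Combined protocol and SAP*

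**What the plan says.** Section 7.2 states that every participant is randomized centrally through IRT, stratified by prior biologic use (yes/no), and that "Block randomization with fixed block size per stratum will be employed in this study".

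The same section then allows replacement. A participant who discontinues because of an AE is not replaced "unless the AE can be determined to be unrelated to treatment". If someone is replaced after dosing, the newcomer's participant number is formed from the original's, and "The replacement participant will receive the same treatment as the participant being replaced, but a new randomization number will be assigned to him/her". The visible text does not require the newcomer to come from the original's biologic stratum.

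Four other rules bear on this:

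- **Section 7.3, concealment:** "Access to treatment codes will be restricted from all site and Sponsor personnel and participants prior to database lock", with listed exceptions.
- **Section 7.3, unblinding:** a participant who is unblinded for any reason must stop study intervention.
- **Section 10.3:** the Full Analysis Set is everyone randomized and dosed, so a dosed original stays in and the replacement is added.
- **Section 10.4.3:** a missing Week 12 PASI counts as non-response, apart from certain early-termination assessments.

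The documents give no expected number of departures or replacements, and the visible text has no separate analysis rule for replacements. The end of Section 7.2 is cut and may say how the pair's data are handled. The point does not depend on it.

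**The concern.** A replacement gets a new randomization number but no draw of his or her own. Which arms gain participants is decided by who leaves after randomization and, for AEs, by a judgement that the event was unrelated to treatment. Two things are at stake.

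1. **Arm size tied to departures.** An arm that loses more participants by chance also receives more additional ones, which dilutes its non-responders. Its expected response rate is pushed up slightly.
2. **Concealment for a linked replacement.** A site that knows the original's arm knows the replacement's arm before choosing whom to enrol. This can arise when the original was unblinded, so had to stop study drug, then left the study and was replaced.

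**Working it through.** **Arm size.** The per-arm number is not visible. With 120 participants in a 1:1:1:1 ratio it is 120/4 = 30. That reproduces Section 10.2:

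- AE detection: 1 − 0.99^30 = 26.0%, 1 − 0.95^30 = 78.5%, 1 − 0.90^30 = 95.8% (stated 26%, 79%, 96%).
- Largest Clopper-Pearson half-width: 18.7% (stated at most 18.8%).
- Exact two-sided Fisher power at 70% v 10%: 99.88% (stated at least 99%).

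**Bias from inherited arms.** Assumptions: each of 30 originals leaves with probability q and counts as a non-responder; each leaver is replaced once; replacements leave with the same probability; completers respond with probability p. With D ~ Bin(30, q) leavers:

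- Arm rate = [(30 − D)p + D(1 − q)p] / (30 + D)
- Bias = E[arm rate] − p(1 − q)

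The mechanism shows in two cases at p = 0.7, q = 0.1, where the target is 0.63. With D = 0 the rate is 0.70. With D = 6 it is (24 × 0.7 + 6 × 0.63)/36 = 0.572. These average 0.636. Without replacement, D = 6 gives 16.8/30 = 0.56, and the average with 0.70 is exactly 0.63.

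**Bias with a randomized top-up.** Let T be total departures over all four arms, shared equally:

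- Arm rate = [(30 − D)p + (T/4)(1 − q)p] / (30 + T/4)

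Bias in percentage points at p = 0.7:

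| Assumed q (expected leavers of 30) | Inherited arm | Randomized top-up |
|---|---|---|
| 1/30 (1) | 0.07 | 0.02 |
| 0.10 (3) | 0.17 | 0.04 |
| 0.20 (6) | 0.26 | 0.07 |

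The top-up leaves about a quarter, because the number added still depends on departures. For inherited arms the bias is 0.04, 0.10 and 0.15 points at p = 0.4, and 0.01, 0.02 and 0.04 at p = 0.1. Part of it cancels in the treatment difference: at q = 0.1 and 70% v 10%, 0.171 − 0.024 = about 0.15 points.

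**Sensitivity to drift.** Suppose 5% of an active arm and 15% of placebo are replaced, and later recruits respond 10 points more often (assumed). Inherited arms then give an active rate of (28.5 × 0.7 + 1.5 × 0.95 × 0.8)/31.5 = 66.95% and a placebo rate of (25.5 × 0.1 + 4.5 × 0.85 × 0.2)/34.5 = 9.61%. The difference is 57.34 points, against 58.00 without replacement: a shift of −0.66. With 20 points of drift the shift is −1.31. A randomized top-up gives +0.07 and +0.14, and at most +0.22 over the range tried.

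**Known arm.** If a fraction f of an arm is replaced by participants chosen with knowledge of the arm, and their response shifts by s, the bias is s·f(1 − f)/(1 + f). One of 30 with s = 10 points gives 0.31 points. Three of 30 with s = 20 points gives 0.10 × 0.90/1.10 × 20 = 1.64 points. A fresh draw sets this to zero.

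**Error rate and power.** Using the rule in Section 10.4.3 (Fisher if any cell is below 5, otherwise chi-square, taken here without continuity correction), simulated type I error was at most about 0.025 in any scenario, including the worst selection case. Exact power at 70% v 10% is 99.95% with no departures, 99.41% with 6 per arm and no top-up, and 99.94% with 6 added completers per arm.

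**The case against.** The strongest reply is that nothing here changes a decision. The largest modelled bias without drift or selection is 0.26 points in one arm, against a planned difference of 60 points. Section 7.2 states the exception openly, so nobody is misled about what happens. Matched replacement also has a merit: it tends to hold completer counts level across arms. All of this stands, and it is why the weight is low.

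A reader might infer that concealment is broken and that sites can choose whom to enrol by arm. The documents do not support that. Site and sponsor staff are blinded, with listed exceptions. A linked number reveals nothing unless the original's arm is already known. Section 7.3 says many emergencies can be managed without unblinding, "particularly when the emergency is clearly not related to the IP". Section 8.2.1 says of withdrawal that "This is expected to be uncommon", and that "Stopping study intervention is not considered withdrawal from the study", so an unblinded participant who stops drug has not thereby left the study.

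Two other inferences fail. A randomized top-up does not avoid the bias altogether; it reduces it. And nothing visible says replaced originals are dropped from the analysis: the Full Analysis Set definition keeps dosed participants in.

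**Conclusion.** The rule is an explicit exception to the stated randomization, with two small consequences.

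- **Arm rate:** about 0.07 to 0.26 points too high under assumed departure rates of 3% to 20% and 70% response, falling to about 0.02 to 0.07 with a randomized top-up. This rests on dosed originals staying in as non-responders and on one replacement per departure.
- **Concealment:** an uncommon route by which a site could know a replacement's arm, which a fresh draw with an unlinked number closes.

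The departure, drift and selection values are assumptions, because the documents give none. Even the worst drift and selection cases tried stay at 1.3 to 1.6 points. Type I error remains below 5%, and power at the planned effect is essentially unaffected. This is a low-priority improvement, worth making because it is cheap and makes the allocation statement true for everyone; it does not threaten the trial's conclusions.

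**What to change.** In Section 7.2, replace the same-treatment rule with: *any additional participant is enrolled under a new, unlinked number and randomized through IRT within his or her own prior-biologic stratum*. Add that every dosed original stays in the Full Analysis Set under the missing-data rule of Section 10.4.3.

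The cost is a short amendment, with the approvals Appendix 2 requires, and an IRT setting. It needs no more participants than the current rule. The downside is that arm sizes or completer counts may end slightly unequal.

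Deleting replacement altogether would be simpler but not free if a dose works less well than planned. At an assumed 40% v 10%, power under the Section 10.4.3 rule is 72.7% with no departures, 55.0% with 6 per arm and no top-up, and 71.2% with 6 added completers per arm.

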7.3 Blinding

This is a randomized, double-blind, placebo-controlled study. Blinded intervention assignments will be managed using IRT. IP supply will be controlled by IRT at each visit. Access to treatment codes will be restricted from all site and Sponsor personnel and participants prior to database lock for the final analysis with exceptions as specified below. Treatment codes may be shared with sites and participants after finalization of the CSR.

Randomization schedules will be shipped directly to a pharmacist or other individual(s) who will be responsible for the dispensing of blinded study intervention. This (these) individual(s) will be unblinded to study intervention identification but will not be involved in any other aspect of study conduct. The randomization schedules will be maintained in a secure location with access limited to authorized personnel.

Blinding of study intervention assignment is critical to the integrity of this clinical study. However, in the event of a medical emergency or pregnancy in an individual participant in which knowledge of the IP is critical to the participant's management, the blind for that participant may be broken by the investigator. The participant's safety takes priority over any other considerations in determining whether a treatment assignment should be unblinded.

Before breaking the blind of an individual participant's treatment, the investigator should determine that the unblinded information is necessary (ie, that it will alter the participant's immediate management). In many cases, particularly when the emergency is clearly not related to the IP, the problem may be properly managed by assuming that the participant is receiving the IP. It is highly desirable that the decision to unblind treatment assignment be discussed with the Medical Monitor, but the investigator always has ultimate authority for the decision to unblind. The actual task of unblinding can be delegated by the investigator to a designee assigned the task on the Delegation of Authority. The Principal Investigator or appointed designee should only perform the emergency unblinding after the decision to unblind the participant has been documented.

For this study, the method of unblinding for emergency purposes is IRT.

In cases of accidental unblinding, contact the Medical Monitor and ensure every attempt is made to minimize additional disclosure and the impact of unblinding.

Any request to unblind a participant for non-emergency purposes should be discussed with the Medical Monitor.

If a participant is unblinded for any reason, the participant will be discontinued from study intervention.

In case of an emergency, the investigator(s) has unrestricted access to randomization information via the IRT system and is capable of breaking the blind through the IRT system without prior approval from the Sponsor. Following the unblinding, the investigator shall notify the Sponsor Medical Monitor or designee that the unblinding took place as soon as possible.

A scientist in the Non-clinical Disposition and Bioanalysis department or the Sponsor (and/or a designee in the external bioanalytical laboratory) will be unblinded to the randomized treatment assignments to minimize unnecessary bioanalytical analysis of samples. Any results shared by the Non-clinical Disposition and Bioanalysis group with the Sponsor's study team will be blinded to ensure integrity of the study.

Blind break (IRT)	The IRT will be programmed with blind-breaking instructions. In case of an emergency, the investigator has the sole responsibility for determining whether unblinding of a participant's intervention assignment is warranted. Participant safety must always be the first consideration in making such a determination. If the investigator decides that unblinding is warranted, the investigator should make every effort to contact the Sponsor prior to unblinding a participant's intervention assignment unless doing so could delay emergency treatment of the participant. If a participant's intervention assignment is unblinded, the Sponsor must be notified within 24 hours after breaking the blind. The date and reason that the blind was broken must be recorded in the source documentation and CRF, as applicable.
Blinded study with unblinded site pharmacist who is dispensing drug	Participants will be randomly assigned in a 1:1:1:1 ratio to receive study intervention. Investigators will remain blinded to each participant's assigned study intervention throughout the study. To maintain this blind, an otherwise uninvolved third party will be responsible for the reconstitution and dispensation of all study intervention and will endeavor to ensure that there are no differences in time taken to dispense study intervention following randomization. This third party will instruct the participant to avoid discussing the taste, dosing frequency, or packaging of the study intervention with the investigator. In the event of a Quality Assurance audit, the auditor(s) will be allowed access to unblinded study intervention records at the site(s) to verify that randomization/dispensing has been done accurately.

Abbreviations: CRF, Case Report Form; IRT, Interactive Response Technology.

